Appendix 04: The effect of LNS on physical activity (added on 24.05.2013)

Table of Contents

1	Stu	dy objectives
2	Hy	potheses to be tested
3	De	finition of the physical activity outcomes
4	Ba	sis for the analysis: Intention to treat and per protocol
5	Tir	ne points for the analyses
6	Pre	sentation of the study findings and hypothesis testing
	6.1	Success of enrolment, follow-up and physical activity measurement
	6.2	Baseline information
	6.3 group	Comparison of physical activity between intervention groups versus the control 4
7	Ge	neral notes on statistical methods
	7.1	Software
	7.2	Preparing physical activity data for analysis
	7.3	Preparing anthropometric data for analysis
	7.4	Multiple comparisons
	7.5	Confidence intervals
	7.6	Interaction and effect modification
	7.7	Covariate adjustment
8	Re	ferences
9	Leg	gends to the figures
10	Fig	ures
	Figur	e 1. Participant flow
	Figur	e 2. Box-Whisker plots of time in moderate-to-vigorous physical activity by groups 8
Та	bles.	
Тε	ble 1	Baseline characteristics of participants at baseline and 18 months
	Table	2 Physical activity at the trial groups

1 Study objectives

The main aim of sub-study is to assess impact of LNS supplementation on physical activity of children at the age of 18 months. This will be done by comparing physical activity of children in the six intervention groups: dietary supplementation with 10 g, 20 g or 40 g/day milk-containing LNS, 20 g or 40 g/day milk-free LNS or nothing (delayed intervention).

A secondary aim is to assess dose response between LNS supplementation and physical activity. In addition, we will explore possible effect modifiers of the impact of LNS supplementation on physical activity.

2 Hypotheses to be tested

The mean physical activity of infants provided with 10, 20, or 40 g/day of LNS from 6 to 18 months of age is greater than that of infants who receive no dietary intervention at the same age.

3 Definition of the physical activity outcomes

Primary outcome: mean accelerometer counts

Physical activity counts used in the analysis are vector magnitude counts, calculated by taking the square root of the sum of squared activity counts of each three axis. The mean counts/15 s of each day will be averaged over all valid days to produce mean of means for each participant.

Data for physical activity will be considered missing if the actual measurement date was over 30 days from the target date.

Secondary outcomes

Percentage of time spend in moderate-to-vigorous physical activity (MVPA) is averaged over all valid days and the averaged value (per participant) is used in the analysis. MVPA is defined in two ways: 1) with vector magnitude counts of $\geq 208/15$ s ([name] et al, unpublished) and 2) with vertical axis activity counts ≥ 419 counts/15 s (Trost et al. 2011). [name] vector magnitude cut point is used because it is the only cut point developed for vector magnitude for children this age. Trost cut point for vertical axis is used to allow comparison with previous studies using that cut point and older models of accelerometers with only vertical axis readings.

For mean vertical axis accelerometer counts/15 s, mean counts of each day are averaged over all valid days and the average value is used in the analyses.

4 Basis for the analysis: Intention to treat and per protocol

The basis for the analysis will be the same as for the primary outcomes, i.e. intention-to-treat analysis for all except for the six participants who were accidentally allocated to another group than actually randomized. Those six participants will be analyzed in the group that they were erroneously allocated to.

5 Time points for the analyses

All the above analyses will be done at the end of the intervention (when the participants are 18 months old).

6 Presentation of the study findings and hypothesis testing

6.1 Success of enrolment, follow-up and physical activity measurement

All registered participants and the success of their follow-up, including physical activity measurement, will be described in a flow chart (Figure 1). For additional information, dropout rate (including participants for whom enough accelerometer data was not available) between groups will be tested with Fisher's exact test and baseline characteristics of dropouts compared to those who completed the study will be tested with t-test or Fisher's exact test. P-values for these tests will be shown in the text.

6.2 Baseline information

Participant characteristics at the trial enrollment (age of 6 months) and at physical activity measurement (at 18 months) will be tabulated by treatment arms as indicated in Table 1. Hypothesis testing will be performed for baseline information to give additional information but p-values will not be presented in Table 1 of the eventual manuscript. Methods used for hypothesis testing are indicated in Table 1.

6.3 Comparison of physical activity between intervention groups versus the control group

Box-whisker plots of the mean vector magnitude accelerometer counts/15s of all 6 groups will be shown side by side in Figure 2. The group means and standard deviations for the mean counts and % of time spend in MVPA for vector magnitude and vertical axis will be presented as indicated in Table 2. The table will also tabulate the difference in activity indicators (mean vector magnitude counts, mean vertical activity counts, % time in MVPA) and their 95% confidence intervals between the control group and each of the intervention groups.

The activity indicators in each of the intervention groups will be individually compared against that of the control group using two-sample t-test. The raw P-values are presented in the tables and text. In addition, the P-values adjusted to multiple comparisons with Holm's method will be presented in the text for the main outcome, mean vector magnitude accelerometer counts/15 s.

Page 5 of 10

7 General notes on statistical methods

7.1 Software

All analyses will be done in Stata/IC version 11. The WHO 2006 multi-centre growth standard will be used for age-and-sex standardization of weight, length (height), weight-for-height, MUAC and head circumference.

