11.2 Baseline information

Participant characteristics at enrollment will be tabulated by treatment arms as indicated in tables 1a and 1b. Hypothesis testing will be performed for baseline information to give additional information but p-values will not be presented in Table 1 of the eventual manuscript. Methods used for hypothesis testing are indicated in Tables 1a and 1b.

11.3 Comparison of the change in length-for-age Z-score between intervention groups versus the control group

Box-whisker plots of the change in LAZ of all 6 groups will be shown side by side in Figure 2. The group means and standard deviations for the change in length (in cm) and LAZ (in z-score units) will be presented as indicated in Table 2. The table will also tabulate the difference in mean length and LAZ and their 95% confidence intervals between the control group and each of the intervention groups.

Mean change in LAZ in each of the intervention groups will be individually compared against that of the control group using a two-sample t-test. The Holm's method will be used to adjust for the multiple comparisons (Aickin & Gensler, 1996). The raw P-values are presented in tables but the text and conclusion will be based on the Holm-adjusted P-values.

The null-hypothesis of LNS having no impact on linear growth is rejected for each comparison that yields a Holm's adjusted p-value <0.05.

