12.2 Preparing anthropometric data for analysis

All the anthropometric measurements were completed in triplicate during each study visit. But for the analysis, the team will use the mean of the first two readings if they do not differ more than by a pre-specified tolerance limit. If they do, the third measurement will be compared with the first and second measurements and the pair of measurements that has smaller difference will be used to calculate the mean which will be used in analyses. If there are only one or two repeated measurements mean of those two will be used for the analyses.

The agreed tolerance limits between the first two measurements are:

- 1. length/height ≤ 0.5 cm
- 2. circumferences (head, MUAC) ≤ 0.5 cm
- 3. infant/child weight ≤ 0.1 kg
- 4. adult weight ≤ 0.1 kg
- 5. skinfold thickness $\leq 2.0 \text{ mm}$

The length, circumference and skinfold thickness measurements were recorded to last complete unit (mm). To account for the bias of always rounding the values a bit downwards, half a unit will be added to all length, circumference and skinfold thickness measurements prior to the analysis. This procedure is not done for weight measurements, since they were recorded accurately with electronic scales.

Missing growth values will be treated as missing, i.e. there will be no growth data imputation from the other data. Imputation is considered unreliable due to long time-interval between anthropometric measurements, at an age when growth faltering is common.

When measuring change in anthropometric values between two time intervals, the change will be treated as missing if there is a missing value in either of the respective time points.

12.3 Multiple comparisons

The study involves multiple objectives and therefore multiple sets of hypothesis. Statistically, the different sets of hypotheses are considered independent families of hypotheses. Statistical adjustment for multiple comparisons in one family of hypotheses does not need to consider the other families.

For efficacy analysis, each family consists of 5 hypotheses, each comparing an intervention group versus the control group. The Holm's adjustment method is used.

For safety analysis, it is preferable to err on the cautious side (Nauta, 2010). We began with testing the global null hypothesis of no difference between groups. If the global null hypothesis is rejected, raw P-values are used in the comparisons between intervention and control groups.

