7.2 Preparing physical activity data for analysis

Data that was originally compiled by ActiLife software (version 5) from ActiGraph GT3X+ devices, will be extracted and combined using the following procedure:

- .gt3x files are converted to .agd files (with 3 axes and 15s epoch length) in ActiLife software
- .agd files are converted to .csv files in ActiLife software
- .csv files brought to StataIC software (version 11) and compiled to the same .dat file.
- Strings of consecutive zeroes of 20 minutes or more are deleted as well as night time (between 8:00 p.m. and 5:00 a.m.)
- First and last day are also deleted as incomplete days

The data is used for the analyses if the participant has minimum of 4 days of minimum of 6 hours of data.

7.3 Preparing anthropometric data for analysis

The same as for the primary outcome analysis

7.4 Multiple comparisons

The same as for the primary outcome analysis

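### Appendix 4 adopts the Holm rule in section 7.4, but section 6.3 reports raw P-values in tables and text, adds Holm for one of four activity measures only, and never says which P-value decides

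*SAP*

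**What the plan says.** Appendix 4 defines one primary activity outcome, mean vector magnitude counts. It has three secondary measures: mean vertical-axis counts, and the percentage of time in moderate-to-vigorous physical activity (MVPA) by each of two cut-points. Section 6.3 compares each of the five LNS groups with control on every measure by two-sample t-test.

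- **Appendix 4, section 6.3**, on reporting: "The raw P-values are presented in the tables and text". It continues: "In addition, the P-values adjusted to multiple comparisons with Holm's method will be presented in the text for the main outcome", namely mean vector magnitude counts. It gives no significance level and no rejection rule.
- **Appendix 4, section 7.4** (Multiple comparisons), in full: "The same as for the primary outcome analysis". No exception is stated.
- **Main SAP, section 12.3** (Multiple comparisons): "For efficacy analysis, each family consists of 5 hypotheses, each comparing an intervention group versus the control group". Then: "The Holm's adjustment method is used".
- **Main SAP, section 11.3** (the primary LAZ comparison): "The raw P-values are presented in tables but the text and conclusion will be based on the Holm-adjusted P-values". Rejection requires a Holm-adjusted P below 0.05.

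**The concern.** Two sections of one appendix give different accounts of how the same contrasts are treated. Section 7.4 brings in Holm for every efficacy family of five. Section 6.3 leads with raw values and offers Holm as a supplement for one family out of four. It also omits the two elements of main section 11.3 that settle the matter for LAZ: the statement that text and conclusions rest on adjusted values, and the rejection rule. Appendix 1, section 6.1, which follows the same template for secondary growth outcomes, kept both.

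At stake is which activity results are described as effects of LNS. If the deciding P-value is not fixed in advance, it can be chosen once both sets of values are known, and a borderline result can be written up either way while citing the SAP.

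**Working it through.** **1. What each section requires, by measure**

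| Measure | Contrasts with control | Section 7.4 (via main 12.3) | Section 6.3 |
|---|---|---|---|
| Mean vector magnitude counts (main) | 5 | Holm over five | Raw in tables and text; Holm added in text; deciding value not named |
| Mean vertical-axis counts | 5 | Holm over five | Raw only |
| % time in MVPA, vector magnitude | 5 | Holm over five | Raw only |
| % time in MVPA, vertical axis | 5 | Holm over five | Raw only |

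There are 4 × 5 = 20 contrasts. For 3 × 5 = 15 of them the two sections cannot both be followed as written. For the remaining 5 both values are produced and the gap is which one governs.

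**2. Where the two readings part**

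Holm compares the ordered P-values with 0.05/5, 0.05/4, 0.05/3, 0.05/2 and 0.05/1, that is 0.01, 0.0125, 0.0167, 0.025 and 0.05. If the smallest raw P exceeds 0.01, nothing in the family is rejected. So a family whose smallest raw P lies above 0.01 and below 0.05 has at least one nominally significant contrast on raw values and none after Holm.

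Invented examples:
- Raw 0.03, 0.20, 0.40, 0.60, 0.80: smallest Holm value 5 × 0.03 = 0.15. One nominal positive on raw values, none with Holm.
- Raw 0.012, 0.020, 0.030, 0.040, 0.045: 5 × 0.012 = 0.06; 4 × 0.020 = 0.08; 3 × 0.030 = 0.09; the last two are carried up to 0.09. Five nominal positives on raw values, none with Holm.

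**3. Size within one family of five**

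Appendix 4 states no error rate or sample size, so there is no figure of its own to reproduce. The check uses assumed conditions: no true difference in any arm, equal arm sizes, a normal approximation and two-sided tests. The statistic for arm k is Z_k = (T_k − C)/√2, where T_k and C are independent standard normals and C is common to all five, which gives correlation 0.5 between contrasts. From 2 million simulated families:

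- P(smallest raw P < 0.05) = 0.182
- P(smallest raw P < 0.01), the Holm chance of any rejection under the global null = 0.042
- Families with a raw P < 0.05 but no Holm rejection: 0.182 − 0.042 = 0.140

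For reference, five independent tests would give 1 − 0.95^5 = 0.226 on raw values; the shared control lowers this to 0.182.

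**The case against.** The best defence is that section 6.3 only says where P-values are shown. A reader might infer that 6.3 declares a contrast significant when its raw P is below 0.05. The document does not say that: 6.3 has no rejection rule, and nominal significance at 0.05 is the reader's reading. Equally, one might infer that 7.4 itself carries over the sentence basing text and conclusions on adjusted values. That sentence is in main section 11.3, whose counterpart in Appendix 4 is 6.3. The counterpart of 7.4 is main section 12.3, which fixes the family and the method but not the reporting. Both limits stand. For the main measure the sections can therefore be read together: Holm is the method, 6.3 supplies it, and raw values sit alongside. What remains is an unnamed deciding value. Since 6.3 falls under a chapter covering hypothesis testing as well as presentation, that is a real omission.

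It can also be argued that raw values for secondary measures are a deliberate, specific choice that overrides a one-line cross-reference. The choice is defensible, but the appendix does not say that 6.3 prevails, and 7.4 states the contrary without exception. One of the two must change.

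Finally, a reader might pool the 15 secondary contrasts and quote a much larger false-positive rate. The documents do not support using that as the size of this conflict. Main section 12.3 treats different sets of hypotheses as separate families with no adjustment across them, so Holm within each measure would not hold a pooled rate at 5% either. Only the within-family comparison isolates the issue.

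**Conclusion.** The inconsistency is real and needs correcting, within limits. For the three secondary activity measures, 6.3 and 7.4 conflict outright over whether a Holm adjustment is made. For mean vector magnitude counts, both values will be reported but the appendix does not say which supports the conclusion. Per measure, the chance of at least one false positive is about 18% if raw values are read at 0.05 and about 4% with Holm; the two readings disagree on whether anything is significant in about 14% of null families. These rates rest on the global null, equal arms, normality and the usual 0.05 level, none of which Appendix 4 states. They illustrate the size of the gap and are not figures from the plan. The primary LAZ and safety analyses are unaffected.

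**What to change.** **Section 6.3, main measure.** State that raw P-values are shown in the tables, and that text and conclusions for mean vector magnitude counts rest on Holm-adjusted P-values over the five comparisons with control, with rejection at adjusted P < 0.05.

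**Sections 6.3 and 7.4, secondary measures.** For vertical-axis counts and the two MVPA measures, choose one of the following and word both sections to match:

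1. Apply Holm within each measure (family of five), as 7.4 now implies, and say so in 6.3.
2. Write an explicit exception into 7.4: these measures are unadjusted and supportive, and no claim of significance is made from them.

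Either resolves the conflict. The cost is SAP wording and, under the first option, 15 additional adjusted P-values from tests already planned. Some contrasts with raw P below 0.05 would no longer be called significant.

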7.2 Preparing physical activity data for analysis

Data that was originally compiled by ActiLife software (version 5) from ActiGraph GT3X+ devices, will be extracted and combined using the following procedure:

- .gt3x files are converted to .agd files (with 3 axes and 15s epoch length) in ActiLife software
- .agd files are converted to .csv files in ActiLife software
- .csv files brought to StataIC software (version 11) and compiled to the same .dat file.
- Strings of consecutive zeroes of 20 minutes or more are deleted as well as night time (between 8:00 p.m. and 5:00 a.m.)
- First and last day are also deleted as incomplete days

The data is used for the analyses if the participant has minimum of 4 days of minimum of 6 hours of data.

7.3 Preparing anthropometric data for analysis

The same as for the primary outcome analysis

7.4 Multiple comparisons

The same as for the primary outcome analysis

7.5 Confidence intervals

The same as for the primary outcome analysis

7.6 Interaction and effect modification

The following variables will be tested for interaction between the intervention group and the primary outcome (mean vector magnitude accelerometer counts). All tests will be done using the likelihood ratio test. The variables tested could logically modify the effect of the nutritional intervention on infancy and physical activity. Variables included (as continuous variables where possible) in this analysis include:

- 1. The participant's baseline length-for-age (below / above sample median) at 6 months
- 2. The participant's baseline weight-for-length (below/above sample median) at 6 months
- 3. The participant's sex
- 4. Season of participant's birth
- 5. Maternal education
- 6. Maternal age
- 7. Household food security

If a statistically significant interaction (p<0.1) is found, the outcome analysis will be completed as stratified by the respective predictor variable.

7.7 Covariate adjustment

The main analysis, the results of which will be shown in tables and figures, will be completed without any covariate adjustments.

As a secondary analysis we will construct a regression model for physical activity, adjusting for the participant's LAZ and WHZ at 6 enrolment, sex, season of enrolment, maternal education, maternal age, and household food insecurity. However, if any of these variables is found to be an effect modifier (see chapter 7.6), it will not be included in the model.

As a sensitivity test for the latter analysis, we will use two alternative methods to build the regression model:

- 1. Inclusion in the model of also the effect modifiers and respective interaction terms.
- 2. Inclusion in the model of only those variables that are associated with physical activity (mean vector magnitude accelerometer counts) at p<0.1 level) with.

8 References

9 Legends to the figures

Figure 1. Participant flow

Figure 2. Box-Whisker plots of time in moderate-to-vigorous physical activity by groups

10 Figures

Figure 1. Participant flow

TablesTable 1 Baseline characteristics of participants at baseline and 18 months

Variable	Control	10g milk LNS	20g milk LNS	20g milk- free LNS	40g milk LNS	40g milk- free LNS	Test
Number of participants	XXX	XXX	XXX	XXX	XXX	XXX	
Mean (SD) maternal age at trial enrollment, years	xx.x (xx.x)	ANOVA					
Mean (SD) maternal education at trial enrollment, completed years at school	x.x (x.x)	ANOVA					
Proportion of food insecure households at trial enrollment	xx.x%	xx.x%	xx.x%	xx.x%	xx.x%	xx.x%	Fisher's exact test
Percentage of males	xx.x%	xx.x%	xx.x%	xx.x%	xx.x%	xx.x%	Fisher's exact test
Season of child's birth	I: xx.x% II: xx.x% III: xx.x% IV: xx.x%	Chi- squared					
Mean (SD) age at physical activity measurement, months	xx.x (xx.x)	ANOVA					
Mean (SD) length-for-age z-score at trial enrollment	XX.XX (XX.XX)	ANOVA					
Mean (SD) length-for-age z-score at physical activity measurement	xx.xx (xx.xx)	ANOVA					
Mean (SD) weight-for-length z-score at trial enrollment	xx.xx (xx.xx)	ANOVA					
Mean (SD) weight-for-length z-score at physical activity measurement	xx.xx (xx.xx)	ANOVA					

Table 2 Physical activity at the trial groups

Variable	Control	10g milk LNS	20g milk LNS	20g milk- free LNS	40g milk LNS	40g milk- free LNS
Mean (SD) vector magnitude accelerometer counts/ 15 s	xxx (xx)	xxx (xx)	xxx (xx)	xxx (xx)	xxx (xx)	xxx (xx)
Difference (95% CI) in mean vector magnitude accelerometer counts between the indicated intervention and the control group.		xx.x (xx.x to xx.x), p=x.xxx	xx.x (xx.x to xx.x) p=x.xxx	xx.x (xx.x to xx.x) p=x.xxx	xx.x (xx.x to xx.x) p=x.xxx	xx.x (xx.x to xx.x) p=x.xxx
Mean (SD) vertical axis accelerometer counts/15 s	xxx (xx)	xxx (xx)	xxx (xx)	xxx (xx)	xxx (xx)	xxx (xx)
Difference (95% CI) in mean vertical axis accelerometer counts between the indicated intervention and the control group.		xx.x (xx.x to xx.x) p=x.xxx	xx.x (xx.x to xx.x) p=x.xxx	xx.x (xx.x to xx.x) p=x.xxx	xx.x (xx.x to xx.x) p=x.xxx	xx.x (xx.x to xx.x) p=x.xxx
Mean (SD) % of time in MVPA, vector magnitude	xx.x (x.x)	xx.x (x.x)	xx.x (x.x)	xx.x (x.x)	xx.x (x.x)	xx.x (x.x)
Difference (95% CI) in % of time in MVPA, vector magnitude, between the indicated intervention and the control group.		xx.x (xx.x to xx.x) p=x.xxx	xx.x (xx.x to xx.x) p=x.xxx	xx.x (xx.x to xx.x) p=x.xxx	xx.x (xx.x to xx.x) p=x.xxx	xx.x (xx.x to xx.x) p=x.xxx
Mean (SD) % of time in moderate-to-vigorous physical activity, vertical axis	xx.x (x.x)	xx.x (x.x)	xx.x (x.x)	xx.x (x.x)	xx.x (x.x)	xx.x (x.x)
Difference (95% CI) in % of time in MVPA, vertical axis, between the indicated intervention and the control group.		xx.x (xx.x to xx.x) p=x.xxx	xx.x (xx.x to xx.x) p=x.xxx	xx.x (xx.x to xx.x) p=x.xxx	xx.x (xx.x to xx.x) p=x.xxx	xx.x (xx.x to xx.x) p=x.xxx

MVPA, moderate-to-vigorous physical activity

Prevention of Linear Growth Faltering in Infants and Young Children With Lipid-based Nutrient Supplements (iLiNS-DOSE)

Statistical Analysis Plan

Appendix 05: Effect on infant and young child feeding practices (version 1.0 added on 26.07.2013, revised to version 2.0 on 28.04.2014)

Contents

Co	ntents2
1.	Version history
2.	Overview and study objectives
